Buspirone for Functional Dysphagia - Protocol

Introduction

Functional Dysphagia has been defined by the Rome Criteria as a syndrome in which patients report symptoms of dysphagia without evidence of GERD and without any histopathology-based esophageal motility disorder. (Rome Criteria) Ineffective Esophageal Motility is a manometric diagnosis (based on the Chicago Classification) without a histopathology correlate which has been shown to cause dysphagia. (Kahrilas, PJ) Data related to treatment of this disorder are limited. Buspirone is a serotonin modulating anxiolytic and antidepressant medication with a reliable safety profile, which has been shown to improve esophageal motility. (Blonski W) We plan to perform a prospective randomized double-blind crossover style placebo controlled trial of the effect of buspirone on patients with functional dysphagia and ineffective esophageal motility.

Background and Significance

Functional Dysphagia has been defined by the Rome Criteria as a syndrome in which patients report symptoms of dysphagia without evidence of GERD and without any histopathology-based esophageal motility disorder. (Rome Criteria) Ineffective Esophageal Motility (IEM) is a manometric diagnosis (based on the Chicago Classification) without a histopathology correlate which has been shown to cause dysphagia. (Kahrilas, PJ)

While the etiology of functional dysphagia is widely debated, there are data that argue that ineffective esophageal motility is the manometric correlate of functional dysphagia. In a study of about 200 patients, Roman, et al. showed that patients with history of dysphagia without any other structural abnormalities were 3-6 times more likely to have ineffective esophageal motility. (Roman S 2011). Furthermore, the prevalence of IEM in functional dysphagia increases with age and has been found to be up to seven times as high in patients above the age of 70 compared to patients below 70. (Ratuapli, SK) IEM may also be partially responsible for the pathogenesis of Gastro-esophageal Reflux Disease (GERD) because of poor acid clearance from the esophagus. (Martinucci I et al, Ribolsi M et al, Savarino E et al, and Fouad YM et al). Data about treatment of IEM are limited. Bethanechol has been tested in this patient population. Agrawal, et al studied seven patients diagnosed with IEM were treated with 50 mg of bethanechol before repeat manometry was performed by providers who were blinded to the experiment. Bethanecol in this population caused an increase in the contractility of the esophagus as well as complete bolus clearing. (Agrawal A) In addition, one study showed that buspirone, pyridostigmine, or bethanechol administration in healthy volunteers causes enhances contractility in the distal esophagus. (Blonski W) While there are no data which have studied medical management of functional dysphagia, functional gastrointestinal disorders of the upper gastrointestinal tract have been treated extensively with antidepressants and anxiolytics, especially buspirone. Functional dyspepsia, for example, is a disorder of gastric motility without histopathologic abnormality on endoscopy. A double-blind randomized controlled crossover style trial of buspirone in this disorder showed increased gastric accommodation, which was correlated with symptom improvement in patients with functional dyspepsia. (Tack J) There are no consensus guidelines for the treatment of functional dysphagia or ineffective esophageal motility. However, various experts argue for the utility of antidepressants and anxiolytic medications for treatment of these disorders. [name], Chairman of the Functional Esophageal Disorders Committee for Rome Criteria IV, says, "...antidepressants are likely to remain the mainstay of treatment of functional esophageal disorders..." (Weijenborg RA et al and Maradey-Romero C) Based on the above observations, we suspect that patients with IEM treated with buspirone will experience improvement in esophageal motility, dysphagia, and GERD.

Study Design

Methods

Randomized Double-Blind Crossover Placebo controlled prospective trial

Sample

Inclusion Criteria: >18 years old, diagnosis of IEM, negative EGD or barium swallow, biopsies negative for EOE Exclusion Criteria: Have not had any changes to serotonin modulating medications over the last 6 weeks This is a cross-over style study and all participants will be both studied in the treatment and control arms.

NCT: 02674412

Version Date: 08/10/2016

Previous studies have shown up to a 100% improvement in baseline manometric findings in patients treated with buspirone. We hope to show at least a 25% difference with a p<0.05 and power 0.8. To show this effect, we will need 15-20 patients (depending on the standard deviation of the specific marker being tested).

Research Procedures – Define the data to be collected to answer the hypothesis/research question(s)

Nurses at the Swallowing Center facilitate the final read by a licensed physician of all manometries performed here. For every patient diagnosed with functional dysphagia and IEM who meets the inclusion and exclusion criteria, the nurses will notify the investigators. Review of electronic charts for all patients undergoing manometry is part of the routine medical practice and responsibility of the nurses. The nurses will also seek the patient's permission to be contacted to hear about the details of an ongoing study related to their diagnosis.

Once the investigators are notified of this diagnosis, one of the investigators will contact the patient to discuss the logistics of the study as well as obtain informed consent. After informed consent is obtained, patients will be randomized to either group A or group B. Both patients and investigators will be blinded to the assignment. All patients will be administered a Mayo Dysphagia Questionnaire as well as a validated GERD questionnaire. Subsequently, all patients in Group A will receive placebo and Group B will receive buspirone administered by pharmacy.

After two week of treatment, all patients will undergo repeat administration of questionnaires as well as assessment of side effects. They will also undergo repeat manometry. All participants will be reimbursed with \$100 for travel expenses.

Subsequently, all patients will be treatment free for a washout period of two weeks.

Patients in Group A will then be treated with buspirone and Group B will be treated with placebo for two weeks followed by repeat questionnaires and manometry. All participants will be reimbursed with another \$100 for travel expenses.

All participants will be contacted by phone one week after they start their treatments to assess for tolerability and side effects related to the medication.

The two interventions that are part of the study are buspirone as well as the two subsequent manometries. Both costs will be incurred by the investigators.

Data Analysis

Descriptive statistics will be computed for all variables. This includes means, standard deviation and percentiles for continuous variables and frequencies and percentages for categorical factors the t test and odds ratio will be calculated for comparison. All analyses will be performed using SAS (version 9.2, The SAS Institute, Cary, NC). The analysis will be completed by one of the investigators.

Adverse Events and Data Monitoring Committee(DMC)

This project does not require an independent DMC or DSMB because this is an open-label intervention looking solely at symptom/sign changes related to buspirone.

After two weeks of being on the medication, each patient will be questioned about his/her baseline symptoms, new symptoms, and any side effects related to the medications (specifically the common side effects of buspirone). All Adverse Events will be reported to the IRB using the Adverse Event Form.

Consent

The consent interview will take place in private patient rooms at the Swallowing Center.

The consent interview will take place after patients are diagnosed with functional dysphagia or IEM. One of the investigators will discuss the study in detail and answer all questions. The patients will then be provided the opportunity to sign the consent or take time to think about the study before signing or rejecting the study.

The consent will be documented on the informed consent form attached with the application.

NCT: 02674412

Version Date: 08/10/2016

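### The only exclusion criterion is worded as an entry condition, so as written it excludes patients with no recent change in serotonin-modulating medication and admits only those with one

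*Combined protocol and SAP*

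**What the plan says.** Eligibility is set out in two lines of the Sample subsection (Study Design, Methods). The first is "Inclusion Criteria: >18 years old, diagnosis of IEM, negative EGD or barium swallow, biopsies negative for EOE". The second, and the only exclusion, is "Exclusion Criteria: Have not had any changes to serotonin modulating medications over the last 6 weeks". The same subsection gives the planned size: "we will need 15-20 patients".

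Research Procedures says how the lists are used. Nurses at the Swallowing Center screen: "Review of electronic charts for all patients undergoing manometry is part of the routine medical practice and responsibility of the nurses", and "For every patient diagnosed with functional dysphagia and IEM who meets the inclusion and exclusion criteria, the nurses will notify the investigators". After notification, "one of the investigators will contact the patient to discuss the logistics of the study as well as obtain informed consent", and then "After informed consent is obtained, patients will be randomized to either group A or group B".

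The Introduction describes buspirone, the study drug, as itself serotonin modulating. The document gives no rationale for the six-week rule and does not restate it anywhere.

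**The concern.** The sentence describes a state that one would normally require of a participant: no recent alteration in a class of background drugs. It stands under the heading for patients who must be kept out. Heading and sentence therefore point in opposite directions, and a literal application selects the patients that the rule was probably meant to remove.

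This is the only stated control at entry on background serotonin-modulating medication, in a trial of a drug from that class. Two consequences follow. Two staff could decide the same chart in opposite ways and each cite the protocol. And a patient enrolled under the probable intent would, on paper, meet an exclusion, so eligibility could not be audited cleanly against the text.

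**Working it through.** No published figure needs reproducing; the check is one of logic and of reading the document for a correction.

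**Step 1: apply the rule in both directions.** Take a patient who meets the inclusion criteria. Let C be true if any serotonin-modulating drug was changed within the six weeks.

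- As written: exclude if C is false.
- Probable intent: exclude if C is true.

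| Background state | C | As written | Probable intent |
|---|---|---|---|
| No such drug throughout the six weeks | false | excluded | admitted |
| Stable on such a drug | false | excluded | admitted |
| Changed within six weeks (including started or stopped) | true | admitted | excluded |

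As written, 1 of the 3 states is admitted and 2 are excluded; under the probable intent, 2 are admitted and 1 is excluded. All 3 are sorted oppositely, and 0 are admitted under both rules. These are counts of states, not shares of patients. They restate that a rule and its negation are complementary.

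**Step 2: set this against the planned sample of 15 to 20.** If screening followed the probable intent, every enrolled patient has C false and so meets the written exclusion: 15 of 15 to 20 of 20. If the text were followed literally, every enrolled patient has C true, so those on a stable regimen or on no such drug number 0 of 15 to 0 of 20.

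**Step 3: look for a correction elsewhere.**

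- The inclusion list covers age, the IEM diagnosis, a negative EGD or barium swallow, and biopsies. It says nothing about medication.
- The word *serotonin* occurs twice in the document: once in this criterion and once in the Introduction's description of buspirone. Neither use shows the intended direction.
- The screening sentence in Research Procedures speaks of a patient who meets both sets of criteria. It can be read as satisfying each listed statement (which would pass a stable patient) or, idiomatically, as being eligible under both headings (which would reject that patient). It does not settle the matter.
- The steps stated after notification are contact, consent and randomisation. None names a further eligibility check at which a misreading would be caught.

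**Step 4: rule out a reading artefact.** The heading and sentence are intact, with no redaction mark or gap. The text runs on after the inclusion list and again after the exclusion, which fits lost line breaks. Nothing suggests that words were lost or reversed.

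**The case against.** The best reply is that this is an evident slip that few screeners would follow. The sentence's own wording signals an entry condition. If the screening instruction is read as literally as the heading, a patient meets the listed statement by having had no change and is referred. On that reading the only operating instruction already delivers the probable intent, and the literal outcome needs the heading read strictly and the screening sentence read loosely. It is also fair to say that the counts of states are not an effect size, that nothing shows staff actually disagreed, and that high confidence belongs to the contradiction in the text rather than to its consequences in practice.

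Much of this stands. Actual screening is not shown, the practical risk is possible rather than demonstrated, and the counts show only that the two rules are complementary. But the screening sentence can be read either way, so it does not repair the rule, and a probable intent is not a written one. Even if every nurse read it as intended, the enrolled patients would meet the protocol's sole exclusion as it stands. The objection limits the severity; it does not remove the error.

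**Conclusion.** The concern holds. The sole exclusion criterion is wrong as written: under its heading it removes otherwise eligible patients with no recent change in serotonin-modulating medication and admits only those with one. The two readings share no patient, so the discrepancy touches the eligibility of all 15 to 20 planned participants. Its effect on the estimate or on power cannot be quantified from the document, and none is claimed.

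The contradiction itself rests on no outside assumption. That the rule was meant to keep out recent changes is an inference from the wording, since no rationale is given. The plan says "The consent will be documented on the informed consent form attached with the application"; that form is not among the documents supplied, so whether it words the rule differently is unknown. The point should be fixed, but it is a correction of text and not a flaw in the design.

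**What to change.** The sponsor should first confirm which patients the rule was meant to keep out, and which direction was used for anyone already screened. If the intent is to keep out recent changes, either of two equivalent edits reconciles the text: move the sentence unchanged to the inclusion criteria, or leave it under exclusion and remove the negation. The nurses' screening wording should then match the protocol. If the intent is otherwise, the protocol should say so and give the reason.

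As a separate and minor clarification, the same edit could state the date from which the six weeks are counted, which the text does not give.

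The cost is a one-sentence protocol correction and matching screening wording, with no extra patients or procedures.

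### The only exclusion criterion is worded in reverse, and once corrected it would still let in a patient on an unchanged buspirone dose

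*Combined protocol and SAP*

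**What the plan says.** Under Study Design, Sample, the protocol gives four inclusion items (age, diagnosis of IEM, a negative endoscopy or barium swallow, and biopsies negative for EOE). None concerns medication. The only exclusion item is "Exclusion Criteria: Have not had any changes to serotonin modulating medications over the last 6 weeks".

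Under Research Procedures the criteria are put to work by nurses: "For every patient diagnosed with functional dysphagia and IEM who meets the inclusion and exclusion criteria, the nurses will notify the investigators". The same paragraph adds: "Review of electronic charts for all patients undergoing manometry is part of the routine medical practice and responsibility of the nurses". An investigator then contacts the patient, consent is obtained and randomisation follows. According to the Consent section, "One of the investigators will discuss the study in detail and answer all questions".

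The design is a crossover in which "all participants will be both studied in the treatment and control arms". Between the two treatment periods, "all patients will be treatment free for a washout period of two weeks". The Introduction places the study drug in the class that the exclusion item refers to: "Buspirone is a serotonin modulating anxiolytic and antidepressant medication with a reliable safety profile".

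The sample size statement is: "We hope to show at least a 25% difference with a p<0.05 and power 0.8", for which 15-20 patients are said to be needed, depending on a standard deviation that is not given.

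**The concern.** An exclusion item lists what keeps a patient out. Here, what keeps a patient out is having had no recent change in serotonin-modulating medication. That removes stable users and non-users, the patients one would want, and keeps the unstable ones. If the rule were followed, a recent changer could carry a continuing effect of that change into the trial. Outcomes are taken at the end of week 2 and the end of week 6 (2 weeks of treatment, 2 of washout, 2 of treatment), so the effect need not be equal in the two periods. With random order this is mainly added noise rather than bias. If staff follow the likely intent instead, every such enrolment contradicts the written protocol.

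The second part remains after the wording is put right. A rule about change does not address current use of the study drug. A patient on a steady buspirone dose has no true placebo period and no drug-free washout, so that patient's buspirone-minus-placebo contrast shrinks. In a trial of 15-20 patients, one such enrolment can be visible in the power. Stable use of other serotonin-modulating drugs is present in both periods and is not the issue.

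**Working it through.** **Step 1. The rule as written and as corrected.**

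| Patient | As written | With the sense reversed |
|---|---|---|
| Takes no serotonin-modulating drug | excluded | eligible |
| Stable on another such drug | excluded | eligible |
| Changed such a drug within 6 weeks | eligible | excluded |
| Buspirone, dose unchanged for more than 6 weeks | excluded | **eligible** |
| Buspirone, started or changed within 6 weeks | eligible | excluded |

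No other statement in the protocol corrects the wording, bars current buspirone use, or says what happens to a patient's own buspirone during the placebo period or washout.

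**Step 2. The plan's own figure.** Inputs from the Sample section are a difference of 25%, p<0.05, power 0.8 and N of 15-20. No standard deviation is given, so N cannot be reproduced. I assume a paired two-sided t test at 0.05 with power exactly 0.80 at the stated N, and solve for the standardised difference d (mean within-patient difference divided by its SD). Power is the probability that a noncentral t with N-1 degrees of freedom and noncentrality d√N exceeds the two-sided 5% critical value.

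- N=15: d = 0.778, implied SD = 25/0.778 = 32.1%.
- N=20: d = 0.660, implied SD = 25/0.660 = 37.9%.

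**Step 3. Dilution by k stable buspirone users.** Let f be the share of the trial drug's effect that it adds on top of the patient's own supply. The expected mean difference is 25 × (1 − (1 − f) × k/N).

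- k=1, f=0: 25 × 14/15 = 23.33% (N=15); 25 × 19/20 = 23.75% (N=20).
- k=2, f=0: 25 × 13/15 = 21.67%; 25 × 18/20 = 22.50%.
- k=1, f=0.5: 25 × (1 − 0.5/15) = 24.17%; 25 × (1 − 0.5/20) = 24.38%.
- f=1: 25% whatever k is.

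**Step 4. Power.** This was simulated (400,000 runs per case). The k users have expected difference f × 25, the others 25, and all have the same SD.

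| Case | N=15 | N=20 |
|---|---|---|
| No such patient | 0.80 | 0.80 |
| One, trial drug adds nothing | 0.73 | 0.75 |
| One, trial drug adds half | 0.77 | 0.78 |
| Two, trial drug adds nothing | 0.65 | 0.70 |
| Any number, trial drug adds its full effect | 0.80 | 0.80 |

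**The case against.** The strongest reply is that the reversal is an obvious slip: a stability requirement was placed under the wrong heading, and no clinician would turn away everyone who takes no such drug. That is probably right about intent. It does not remove the need to correct a line that serves as the working screening rule. It does rule out one inference a reader might draw, that the trial will in fact enrol only recent changers. The documents do not show how staff apply the item.

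The second reply is that the buspirone user is hypothetical. Only users with no change for six weeks would pass, so it would overstate the point to say that the corrected rule lets in buspirone users generally. Background and Significance says that buspirone is much used for functional disorders of the upper gut, which makes prior use possible. The same sentence says there are no data on medical management of functional dysphagia. Such a patient would also have to go unnoticed at chart review and in a detailed discussion of a buspirone trial. All of this stands, and it is why the power figures are a cost per patient and not a forecast. They also rest on an assumed paired test (Data Analysis says only a t test) and a back-solved SD.

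A reader might go further and infer a safety failure, since no written step before dosing is described as a check for contraindications. The documents do not support that reading. They name no contraindication. The consent form and the application it is attached to are not in the text available. Chart review, the consent discussion or the pharmacy could each catch a problem in ordinary practice.

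**Conclusion.** The point holds in two parts. First, the only exclusion criterion is wrong as written, nothing else corrects it, and nurses screen on it. This follows from the text alone. Second, reversing the sentence would still leave a gap for a patient on an unchanged buspirone dose of more than six weeks' standing.

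The size of the second part is conditional. One such patient costs between nothing and about 7 points of power at N=15 (0.80 to 0.73), or between nothing and about 5 points at N=20 (0.80 to 0.75), depending on how much trial drug adds to the patient's own supply. The expected loss is unknown and may be zero, because the documents do not say how many such patients, if any, would enter. The absence of a listed contraindication exclusion is not shown to be an error.

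**What to change.** In the Sample section:

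1. Replace the exclusion item with: *Exclude patients with any change to serotonin-modulating medication in the last 6 weeks (stable use of other such drugs is allowed).*
2. Add: *Exclude current use of buspirone outside the trial.*

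In Research Procedures, state that both are checked at the existing nurse chart review and confirmed with the patient by the investigator at the existing consent discussion, since a chart may not show medicines obtained elsewhere.

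The cost is one reworded line, one new line and no new visit. A few otherwise eligible patients may be lost. The number cannot be judged from the documents, and it could matter when only 15-20 are sought.

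As a secondary addition, the sponsor could list labelled contraindications to buspirone as an exclusion. That is sensible because every participant is due to receive the drug, but it is a suggestion and not the correction of a demonstrated fault.

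### No primary outcome is named: alpha, power and sample size attach to an unidentified marker, so any one of several outcomes could carry the claim

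*Combined protocol and SAP*

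**What the plan says.** All references are to the combined protocol and SAP.

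- **Study Design, Sample.** Earlier work is said to have shown "up to a 100% improvement in baseline manometric findings". The target follows: "We hope to show at least a 25% difference with a p<0.05 and power 0.8". Then comes the sample size: "we will need 15-20 patients (depending on the standard deviation of the specific marker being tested". The design is a crossover: "This is a cross-over style study and all participants will be both studied in the treatment and control arms".
- **Background and Significance.** The closing sentence expects buspirone to improve oesophageal motility, dysphagia and reflux disease, without ranking them.
- **Research Procedures.** At the start, "All patients will be administered a Mayo Dysphagia Questionnaire as well as a validated GERD questionnaire". Questionnaires and manometry are repeated after the first treatment period, and the second period is likewise "followed by repeat questionnaires and manometry".
- **Data Analysis.** After descriptive statistics for all variables, the only inferential statement is that "the t test and odds ratio will be calculated for comparison". It does not say which variable gets which test.
- **Adverse Events and Data Monitoring Committee.** The study is described as "looking solely at symptom/sign changes related to buspirone", which again does not rank symptoms against manometric signs.

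No section names a primary or secondary outcome, a manometric parameter, a testing order or a multiplicity rule.

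**The concern.** The plan sets a significance level, a power and an effect to be shown, so it presents itself as a hypothesis test. It does not say which test. Manometry is a domain that can yield several parameters, and the sample-size sentence itself makes the number of patients depend on which marker is chosen. The two questionnaires are further candidates.

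Two things are at stake. First, if any single result at p<0.05 may support a claim of benefit, the false-claim rate exceeds that of one test, and the choice of deciding outcome cannot be made soundly once the data are unblinded. Second, a reader cannot tell whether 15-20 patients give 80% power, because the marker and its SD are absent.

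**Working it through.** **Inputs from the plan:** 25% difference, p<0.05, power 0.8, 15-20 patients, each patient studied on both treatments.

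**Assumptions, not in the plan:** two-sided tests; a paired t test; an additive difference, with both the 25% and the SD expressed as percentages of one reference mean; for the error rates, continuous outcomes, three tests (one marker and two questionnaires) or five (three markers and two questionnaires), and a common correlation of 0 to 0.8.

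**1. The plan's own figure.** The 15-20 cannot be reproduced forward, because no SD is given. It can be solved backward. With d = 25 / SD of within-patient differences, power is P(T > t(0.975, n-1)), where T is noncentral t with n-1 df and noncentrality d√n. Setting power to 0.80:

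- n = 15: d = 0.778, so SD = 25 / 0.778 = 32.1%.
- n = 20: d = 0.660, so SD = 37.8% (37.85% from the unrounded d).

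The stated range is therefore consistent with an SD of about 32-38% of the reference mean. A crossover model with n-2 df gives ceilings of 31.9% and 37.7%. One-sided 0.05 tests would give 37.0% and 43.3%.

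**2. How much the unnamed marker matters.** Same test, 25% difference:

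| Assumed SD of differences | Power, n=15 | Power, n=20 | n for 80% |
|---|---|---|---|
| 25% | 95% | 99% | 10 |
| 30% | 85% | 94% | 14 |
| 35% | 73% | 86% | 18 |
| 40% | 62% | 76% | 23 |
| 50% | 44% | 56% | 34 |

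**3. Chance of a false benefit claim if any one outcome suffices.** One two-sided 0.05 test favours buspirone by chance with probability 0.025. For k independent tests the chance of at least one is 1 - 0.975^k:

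- k = 3: 1 - 0.975³ = 0.073.
- k = 5: 1 - 0.975⁵ = 0.119.

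With correlated outcomes (simulation, n = 18, 400,000 replicates):

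| Correlation | 3 tests, any one | 5 tests, any one | All 3 required |
|---|---|---|---|
| 0 | 7.3% | 11.9% | <0.01% |
| 0.3 | 6.9% | 10.7% | 0.04% |
| 0.5 | 6.4% | 9.4% | 0.14% |
| 0.8 | 5.0% | 6.6% | 0.65% |

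Counting a false positive in either direction, the independent values are 1 - 0.95³ = 14.3% and 1 - 0.95⁵ = 22.6%, against 5% for one test. At correlation 0.8 they fall to 10.0% and 13.2%.

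**The case against.** The strongest reply is that manometry is implicitly primary: the sample-size paragraph runs straight from manometric findings to the 25% target to the marker. That stands as far as the domain goes. The certain gap is the parameter within manometry; competition from the questionnaires for the lead claim is less certain. A domain still does not fix a test.

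Four stronger readings are tempting, and the documents do not support them.

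- *That all three domains will be tested confirmatorily.* The Data Analysis section lists no test by outcome, and the background sentence states an expectation. The plan neither permits nor excludes a claim on any single outcome. If it meant that all three must improve, error would not inflate.
- *That the error rates above are estimates for this trial.* They are illustrations. The number of tests and the correlations are assumed, and the planned odds ratios imply that some comparisons are categorical. In a sample this small, such tests need not have a true size of 5%.
- *That 15-20 patients is wrong or the trial underpowered.* The range fits a plausible-looking band of SDs, and nothing in the documents contradicts it.
- *That a null result could not be interpreted.* Its confidence interval, built from the observed within-patient SD, would show whether a 25% difference is excluded. Only the planned power is uncheckable.

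The t test is not said to be paired, but the crossover statement makes a within-patient comparison the natural reading. This is a matter of wording to settle within the same fix.

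**Conclusion.** The point holds and should be fixed before unblinding. As written, the plan does not identify the test that decides the trial, and a result at p<0.05 on any manometric marker or questionnaire could be put forward as the finding. Under the stated assumptions, that roughly doubles or triples the 2.5% chance of a false benefit claim with three outcomes (5-7%), and raises it to 7-12% with five. Under an all-must-succeed rule it would stay below 1%.

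The absence of a named outcome, order or multiplicity rule is a matter of record. The size of the inflation is conditional. On power the conclusion is limited: 80% is neither confirmed nor refuted, because it depends on an SD that the plan does not give.

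**What to change.** Before unblinding, amend the protocol and SAP wording as follows.

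1. **Name one primary outcome.** A single manometric parameter fits the sample-size paragraph; the choice is the sponsor's. Compare buspirone with placebo within patient, by paired t test or crossover model, at two-sided 0.05.
2. **Label all other manometric markers and both questionnaires secondary,** with no confirmatory claim unless a stated multiplicity rule is used.
3. **Restate the sample size,** for example: With [one planned number] completers, power for a 25% difference in [marker], expressed relative to [reference mean], is [x]%, given an SD of within-patient differences of [value, source].
4. **If no SD can be sourced, say what the power rests on.** For a two-sided 0.05 paired t test on an additive difference scaled to the reference mean, 80% power holds only if the SD of within-patient differences is at most about 32% (15 completers) or about 38% (20 completers; 37.8% more exactly). For a crossover model with n-2 df the limits are 31.9% and 37.7%. Power is lower if the SD is larger. These limits do not carry over to a ratio or per-patient percentage-change analysis.

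The cost is wording only, with no new data or visits. The stated power becomes conditional and may turn out below 80%, and the other outcomes become explicitly secondary.
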